Subject characteristics and study results will be described and summarized by treatment arm and assessment for the relevant analysis sets. Descriptive summaries will be prepared to show sample size, mean, standard deviation, 95% confidence intervals (CIs) on the mean, median, minimum, and maximum for continuous variables and counts, percentages, and 95% CIs on the percentage for categorical variables.

An independent review committee (IRC) will review radiographic data and pertinent clinical data in order to provide expert evaluation of tumor status. The findings of the IRC will be considered primary for analyses of PFS and other tumor control endpoints.

For the primary efficacy analysis, the difference in PFS between the treatment arms will be assessed in the ITT analysis set using Kaplan-Meier methods and the stratified log-rank test. Medians, ranges, the proportions of subjects who are progression-free at 24 and 48 weeks from randomization (based on Kaplan-Meier estimates), hazard ratios, and the corresponding 95% CIs (as calculated using a Cox proportional hazards regression model) will be presented.

Secondary endpoints will be ORR, lymph node response rate, OS, PFS in the subgroup of subjects with 17p deletion and/or TP53 mutation, and CR rate. The primary efficacy hypothesis relating to PFS must be rejected at the pre-specified significance level before the efficacy hypotheses for these secondary efficacy endpoints are tested. These 5 secondary endpoints will be tested at the 2-sided 0.03 significance level in the order listed at an interim or final analysis when the primary endpoint is rejected. If a null hypothesis is not rejected, formal sequential testing will be stopped and only nominal significance will be cited for the remaining secondary endpoints.

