#### 1.3.5.2.2. Phase 1 Combination Study in Patients with Hematological Malignancies

A separate Phase 1 trial (Study 101-07) has evaluated the safety and preliminary activity of idelalisib given in combination with ofatumumab to subjects with recurrent CLL {[Barrientos 2012](#), [Furman 2012](#)}.

In this study, idelalisib (150 mg BID) was co-administered with a total of 12 infusions of ofatumumab given over 24 weeks (300-mg initial dose followed 1 week later by 1,000 mg weekly for 7 doses, followed 4 weeks later by 1,000 mg every 4 weeks for 4 doses). Thereafter, subjects continued to receive single-agent idelalisib as long as the subject was safely benefiting from therapy. Subjects were evaluated in 4-week cycles; response and progression assessments were based on standard criteria {[Hallek 2008](#)}.

At the time of the data analysis, accrual of the cohorts was complete with 21 subjects enrolled and evaluable. Median [range] age was 66 [43-79] years. The majority (14/21; 67%) of patients had bulky adenopathy ( $\geq 1$  lymph node  $\geq 5$  cm in diameter). The median [range] number of prior therapies was 3 [1-6], including prior exposure to alkylating agents (18/21; 86%), rituximab (20/21; 95%), purine analogs (16/21; 76%), alemtuzumab (4/21; 19%), and/or ofatumumab (3/21; 14%). The median [range] idelalisib treatment duration was 36+ [0-48+] week.

No idelalisib-related dose-limiting toxicities were observed within the tested subject cohorts. Ofatumumab infusion reactions were manageable. One patient developed corticosteroid-related hyperglycemia and sepsis. No clinically significant myelosuppression was observed.

Almost all subjects (17/21, 84%) experienced marked and rapid reductions in lymphadenopathy within the first 2 cycles. The lymphocyte mobilization that is expected with PI3K $\delta$  inhibition was significantly reduced in magnitude and duration and persisted past Cycle 1 in only 1 patient. The ORR was 16/21 (76%) with 2/21 (10%) subjects showing evidence of complete response (CR), as reported by the investigators. Elevated baseline levels of CCL3, CCL4, CXCL13, and TNF $\alpha$  were significantly reduced after 28 days of treatment. At the time of the data analysis, overall PFS through 48 weeks was >75% and a median PFS had not yet been observed.

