#### **9.2.2. Secondary and Exploratory Endpoints**

The secondary and exploratory endpoints of the study are defined in Section 3.4, grouped in categories relating to tumor control, patient well-being, pharmacodynamic markers of drug activity and resistance, exposure, safety, and pharmacoeconomics.

Of these endpoints, 5 endpoints are designated as secondary endpoints for which sequential testing will be performed to control Type I error rate (see Section 9.4.1.6). These secondary endpoints will be ORR, lymphadenopathy node response rate, OS, PFS in the subgroup of subjects with 17p deletion and/or TP53 mutation, and CR rate. Other endpoints will be considered exploratory.

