#### 9.4.1.6. Control of Type I Error Rate in Efficacy Analyses

In the efficacy analyses, the following procedures will be implemented to preserve the overall type I error rate across the primary and secondary endpoints of the study at a 2-sided significance level of 0.05.

The primary endpoint analysis will serve as the gatekeeper for the secondary endpoint analyses, ie, the primary efficacy hypothesis must be made before the efficacy hypotheses for the secondary efficacy endpoints can be tested. The secondary endpoints will be the following:

- ORR
- Lymphadenopathy node response rate
- CR rate
- OS
- PFS in the subgroup of subjects with 17p deletion and/or TP53 mutation

If the primary hypothesis is rejected, the 5 secondary endpoints will be sequentially tested at the 2-sided 0.03 significance level in the order listed above. If a null hypothesis is not rejected, formal sequential testing will be stopped and only nominal significance will be cited for the remaining secondary endpoints. Analyses and p-values will be reported for all the efficacy endpoints, including the primary endpoint, the secondary endpoints, and all of the exploratory endpoints.

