### 9.5. Sample Size

Based on data from the Phase 2 pivotal study ofatumumab {[Wierda 2010](#)} and considering the population of subjects to be enrolled to this study, it is reasonable to assume that administration of ofatumumab to subjects with previously treated CLL in Arm B of this trial will result in a median PFS of ~8 months. An improvement in median PFS from 8 months to 14 months due to the addition of idelalisib to ofatumumab in Arm A of the study would correspond to a benefit ratio of 1.75 (hazard ratio 0.57).

It is assumed that PFS times are exponentially distributed in each of the 2 arms. With a hazard ratio equal to 1 under the null hypothesis of no difference between the 2 treatment arms and a hazard ratio of 0.57 under the alternative hypothesis of superiority of the idelalisib-containing combination, 129 events (definitive CLL progressions or deaths) are required to achieve a power of >0.85 based on a log-rank test with a 2-sided significance level of 0.05. Further assuming a planned accrual period of 12 months (with approximately half of the subjects enrolled during the initial 60% of the accrual period, and the remaining half of the subjects enrolled during the last 40% of the accrual period), a minimum follow-up period of 12 months, and an expectation that 10% of subjects will be lost to follow-up (5% during the accrual period and 5% during the follow-up period), and to ensure the primary analysis on PFS will be performed before or at the planned minimum 12-month follow-up period, 170 subjects will be enrolled into Arm A and 85 subjects will be enrolled into Arm B in order to achieve the expected number of events by the end of the planned minimum 12-month follow-up period. If the planned subject enrollment does not appear adequate to accrue the expected number of events within the proposed follow-up period, the sample size may be adjusted upward.

It is expected that there will be approximately 65 deaths at the time of final analysis. This would provide ~85% power to detect a HR of 0.45 for overall survival based on a log-rank test at 2-sided alpha level of 0.03.

The resulting safety data set provided by the idelalisib-treated subjects (N=170) compares favorably with the safety data set derived from the initial pivotal registration trials for ofatumumab (N=138) {[Wierda 2010](#)}, oral fludarabine (N=78) {[Boogaerts 2001](#)}, or alemtuzumab (N=93) {[Keating 2002a](#)}.

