## **9.6. Timing of Analyses**

### **9.6.1. Interim Analysis**

The DMC will have access to serious adverse events requiring expedited reporting and will be provided with accumulating safety data on a regular basis. An interim safety review will be conducted by the DMC at ~6 months after the first subject is enrolled. Thereafter, interim safety reviews will be performed by the DMC at intervals of ~6 months; the specific frequency of these reviews will depend upon the rate at which the trial is enrolled, the nature of any emerging safety signals, and monitoring recommendations from the DMC. At each review, all available safety data will be summarized and evaluated.

Two formal interim efficacy analyses for PFS are planned. The first interim analysis will be performed when ~50% of the expected 129 events occur. The second interim will be performed when ~75% of the expected events occur. Type I error rate for testing PFS will be controlled by using the O'Brien-Fleming boundaries. Based on the planned number of PFS events for the 2 interim analyses, the 2-sided alpha for the interim and the final analyses are (0.003, 0.018, 0.044). The significant levels will be recalculated based on the actual observed number of events at the time of the interim and final analyses.

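### The synopsis and Section 9.4.1.6 fix two different test orders for the five secondary endpoints, so whether OS is formally tested can depend on which one is followed

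*Protocol*

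**What the plan says.** **Order in the synopsis.** The Protocol Synopsis, Statistical Methods, lists ORR, lymph node response rate, OS, PFS in the 17p/TP53 subgroup and CR rate. It tests them at two-sided 0.03 "in the order listed at an interim or final analysis when the primary endpoint is rejected".

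**Order in Section 9.4.1.6.** The section on control of type I error lists ORR, nodal response, CR rate, OS and then subgroup PFS. They are "sequentially tested at the 2-sided 0.03 significance level in the order listed above". It does not say at which PFS look this happens.

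**Stopping rule, the same in both places.** "If a null hypothesis is not rejected, formal sequential testing will be stopped", and later endpoints receive only nominal p-values.

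**Other lists.** The synopsis endpoint list, Section 3.4 and Section 9.2.2 name the endpoints in the synopsis sequence; in 9.2.2, after ORR, it reads "lymphadenopathy node response rate, OS, PFS in the subgroup of subjects with 17p deletion and/or TP53 mutation, and CR rate". None of these three states a test order. Sections 3.4 and 9.2.2 send the reader to 9.4.1.6 for the sequential testing.

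**OS power.** Section 9.5 and the synopsis say: "It is expected that there will be approximately 65 deaths at the time of final analysis". Section 9.5 continues: "This would provide ~85% power to detect a HR of 0.45 for overall survival", by a log-rank test at two-sided 0.03. Section 9.6.1 sets PFS looks at about 50%, 75% and 100% of 129 events, with two-sided levels 0.003, 0.018 and 0.044.

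**The concern.** In a fixed-sequence procedure the order is the rule: it decides which hypotheses may be tested at all. Here the protocol states the rule twice and differently, and the section cited elsewhere as the authority disagrees with the synopsis. If the conflict stayed open until results were known, the sequence could be chosen to suit them.

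Take PFS, ORR and nodal response as passed, with no true effect on either CR rate or OS. Either fixed order limits a false claim at the third step to 0.03. A free choice between the two orders gives two chances: at most 0.03 + 0.03 = 0.06, or 1 − 0.97² = 0.059 if the two tests were independent. That is above the overall 0.05 that 9.4.1.6 sets out to protect.

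A second, smaller matter follows from the synopsis rule on timing. The only OS power given is for the final look, while the OS test takes place at whichever look rejects PFS. A reader could take ~85% as the OS power of the procedure as a whole.

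**Working it through.** **1. The two orders side by side**

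| Step | Synopsis, Statistical Methods | Section 9.4.1.6 |
|---|---|---|
| 1 | ORR | ORR |
| 2 | Nodal response | Nodal response |
| 3 | OS | CR rate |
| 4 | Subgroup PFS | OS |
| 5 | CR rate | Subgroup PFS |

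Suppose steps 1 and 2 are passed. The remaining three endpoints have 2³ = 8 pass/fail patterns at 0.03:

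- OS passes, CR fails (2 patterns). Synopsis: OS is claimed and subgroup PFS is tested. 9.4.1.6: testing stops at CR, so neither OS nor subgroup PFS can be claimed.
- OS fails, CR passes (2 patterns). Synopsis: testing stops at OS with nothing further claimed. 9.4.1.6: CR is claimed.
- OS and CR pass, subgroup PFS fails (1 pattern). Synopsis: OS only. 9.4.1.6: CR and OS.
- OS and CR both fail (2 patterns), or all three pass (1 pattern). The two orders give the same claims.

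The claims differ in 2 + 2 + 1 = 5 of 8 patterns. This is a count of patterns, not a probability.

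**2. Reproducing the stated OS power**

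Inputs (Section 9.5): 65 deaths, HR 0.45, two-sided 0.03 (critical value 2.170), 170 versus 85 subjects. Power = Φ(|ln HR|·√(d·r) − 2.170), with |ln 0.45| = 0.7985.

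- Equal-allocation form, r = 1/4: 0.7985 × √16.25 − 2.170 = 1.049, giving 85.3%.
- Event split expected under HR 0.45 with 2:1 allocation (about 0.9:1): 85.2%.
- Simulated log-rank test, 170 versus 85, protocol accrual, 12,000 runs: 84.7%.
- Plain 2:1 form, r = 2/9: 0.7985 × √14.44 − 2.170 = 0.865, giving 80.6%.

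The ~85% is reproduced for 65 deaths.

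**3. The look at which PFS is won**

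Inputs (Sections 9.5 and 9.6.1): HR 0.57, 129 events, information 0.5/0.75/1, critical values 2.968/2.366/2.014. Final drift = −ln(0.57) × √(129 × 2/9) = 0.562 × 5.354 = 3.01. Simulating the three-look test (2 million paths) gives cumulative crossing of 0.201, 0.599 and 0.847. The interim share of wins is 0.599/0.847 = 71%, with about 24% of wins at look 1, 47% at look 2 and 29% at the final look. The interim share is 58% at a PFS HR of 0.65 and 84% at 0.50.

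**4. Deaths and OS power by look**

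The protocol gives no interim death count. Assumptions: exponential OS, HR 0.45, calibrated to 65 deaths at 129 PFS events; half of accrual in 7.2 months and half in 4.8; 10% loss. This implies a control OS median of about 17.5 months and about 29, 46 and 65 deaths. Without conditioning on a PFS win, the formulas in step 2 (2:1 form to equal form) give 44–49%, 65–70% and 81–85%.

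The OS test takes place only after a PFS win, so the relevant figure is conditional. Simulated at a control median of 17.5 months (4,000 runs), and ignoring the tests ranked ahead of OS:

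- PFS and OS independent: 0.705 overall.
- Deaths counted as PFS events, as Section 3.3 defines PFS: 0.806 overall, and 0.83, 0.79 and 0.80 at looks 1, 2 and 3. Early PFS wins select trials that also look favourable on OS.

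**The case against.** On the order, it can be argued that four lists in the protocol (three endpoint lists and the synopsis sequence) agree and only 9.4.1.6 differs. That does not settle it. The three endpoint lists state no test order, and two of them defer to 9.4.1.6. The conflict is one synopsis paragraph against the body section devoted to type I error, and both claim to fix the sequence. A statistical analysis plan could choose one order, but the protocol would still state two.

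On OS power, the objection largely stands. Section 9.5 ties ~85% to about 65 deaths at the final analysis, and that figure is reproduced. Interim power for a secondary endpoint is often left to the analysis plan. That OS is tested only once is also a reading: the synopsis does not say so, although it provides no re-test and Section 9.6.3 offers only supplemental OS follow-up.

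A reader might infer more than the protocol supports:

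- *That OS power collapses at the first look.* The 44–49% is unconditional. With deaths counted as PFS events, power given a win at look 1 is about 83%.
- *That type I error is inflated by testing OS at an interim.* A single OS test at 0.03 at the look that rejects PFS had a maximum error of 0.030 across the PFS effects and correlations tried.
- *That the CR-rate test would probably block OS.* The protocol gives no control CR rate, and its only CR figure for the combination is 2 of 21, investigator-reported, so no useful power can be put on that step.
- *That the 65 deaths belong to a later calendar date.* Sections 9.5 and 9.6.2 word the expected follow-up loosely, but the final analysis is triggered by about 129 events and the 65 deaths attach to it.

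**Conclusion.** The order conflict is established from the text alone and needs no modelling. The two sequences lead to different claims in five of eight patterns once ORR and nodal response have passed. In particular, a failed CR-rate test bars OS and subgroup PFS from formal testing under 9.4.1.6 but not under the synopsis. It should be corrected.

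The OS-power matter is a clarification, not an error. At PFS HR 0.57 about 71% of PFS wins, and so of OS tests under the synopsis rule, fall at an interim, with about 29 or 46 deaths instead of 65. OS power given a PFS win is roughly 70% (PFS and OS independent) to 81% (deaths counted as PFS events), before any loss at earlier tests. The upper figure is closer to the protocol's own PFS definition. Both rest on exponential OS, HR 0.45 and calibration to 65 deaths at 129 events. With control OS medians of 24 to 15 months instead, the range widens to about 58–88%. That range extends above 85%, so a definite shortfall is not shown.

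**What to change.** 1. State one order for the five secondary endpoints, the same in the synopsis (Statistical Methods) and in Section 9.4.1.6, and bring the lists in the synopsis endpoints, Section 3.4 and Section 9.2.2 into line with it. Which order to adopt is the sponsor's choice. It must be fixed before the first unblinded interim efficacy look.
2. Carry into 9.4.1.6 the synopsis rule that the secondary endpoints are tested at the interim or final analysis at which PFS is rejected.
3. As a clarification in Section 9.5 and the synopsis, say that ~85% applies to an OS test at the final look with about 65 deaths, and that an OS test at an interim would rest on fewer.

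The cost is wording in an amendment. Alpha levels, sample size, data collection and the stopping rule for the sequence do not change.

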### Sample Size Calculation

Based on data from prior studies, it is reasonable to assume that administration of ofatumumab to subjects with previously treated CLL in Arm B of this trial will result in a median PFS of ~8 months. An improvement in median PFS from 8 months to 14 months resulting from the addition of idelalisib to ofatumumab in Arm A of the study would correspond to a benefit ratio of 1.75 (hazard ratio 0.57).

It is assumed that PFS times are exponentially distributed in each of the 2 arms. With a hazard ratio equal to 1 under the null hypothesis of no difference between the 2 treatment arms and a hazard ratio of 0.57 under the alternative hypothesis of superiority of the idelalisib containing combination, 129 events (definitive CLL progressions or deaths) are required to achieve a power of > 0.85 based on a log-rank test with a 2-sided significance level of 0.05. Further assuming a planned accrual period of 12 months (with approximately half of the subjects enrolled during the initial 60% of the accrual period, and the remaining half of the subjects enrolled during the last 40% of the accrual period), a minimum follow-up period of 12 months, and an expectation that 10% of subjects will be lost to follow-up (5% during the accrual period and 5% during the follow-up period), and to ensure the primary analysis on PFS will be performed before or at the planned minimum 12-month follow-up period, 170 subjects will be enrolled into Arm A and 85 subjects will be enrolled into Arm B in order to achieve the expected number of events by the end of the planned minimum 12-month follow-up period.

It is expected that there will be approximately 65 deaths at the time of final analysis. This would provide ~ 85% power to detect a HR of 0.45 for overall survival based on a log-rank test on a 2-sided alpha level of 0.03.

### Interim Efficacy Analyses

Two formal interim efficacy analyses for PFS are planned. The first interim analysis will be performed when ~50% of the planned 129 events occur. The second interim will be performed when ~75% of the expected events occur. Type I error rate for testing PFS will be controlled by using the O'Brien-Fleming boundaries. Based on the planned number of PFS events (50% and 75%) for the 2 interim analyses, the 2-sided alpha for the interim and the final analyses are 0.003, 0.018, 0.044. The significant levels will be recalculated based on the actual observed number of events at the time of the interim and final analyses.

---

This study will be conducted in accordance with the guidelines of Good Clinical Practice (GCP), including archiving of essential documents.

## GLOSSARY OF ABBREVIATIONS AND DEFINITION OF TERMS

$\beta$ -HCG	Beta human chorionic gonadotropin
ABCG2	adenosine triphosphate-binding cassette sub-family G member 2 (see also BCRP)
ADCC	antibody-dependent cellular cytotoxicity
AE	adverse event
AKT	AKT (a serine/threonine protein kinase)
ALC	absolute lymphocyte count
ALL	acute lymphocytic leukemia
ALP	alkaline phosphatase
ALT	alanine aminotransferase
ANCOVA	analysis of covariance
ANC	absolute neutrophil count
aPTT	activated partial thromboplastin time
AST	aspartate aminotransferase
AUC	area under the concentration-time curve
ATC	Anatomical-Therapeutic-Chemical classification system for drugs
BCRP	breast cancer resistance protein (see also ABCG2)
BID	twice per day
BTK	Bruton tyrosine kinase
CAL-101	Former name for idelalisib
CCL	chemokine (C-C motif) ligand
CDC	complement-dependent cytotoxicity
CFR	Code of Federal Regulations
CI	confidence interval
CIRS	Cumulative Illness Rating Scale
CLL	chronic lymphocytic leukemia
cGMP	current Good Manufacturing Practice
$C_{max}$	maximum concentration
CMV	Cytomegalovirus
CR	complete response
CRO	contract research organization
CT	computed tomography
CTCAE	Common Terminology Criteria for Adverse Events
$C_{trough}$	trough concentration
CXCL	chemokine (C-X-C motif) ligand
CYP	cytochrome P450 enzyme
DLBCL	Diffuse large B-cell lymphoma
DLCO	diffusing capacity of the lung for carbon monoxide
DMC	data monitoring committee

---

DNA	deoxyribonucleic acid
DOR	duration of response
DSPH	Gilead Sciences Department of Safety and Public Health
ECG	Electrocardiogram
eC Cr	estimated creatinine clearance
eCRF	electronic case report form
EDC	electronic data capture
ELISA	enzyme-linked immunosorbent assay
EQ-5D	EuroQoL Five-Dimension utility measure
FACT-Leu	Functional Assessment of Cancer Therapy: Leukemia questionnaire
FCεRI	high-affinity IgE receptor
FDA	United States Food and Drug Administration
FDAMA	Food and Drug Modernization Act
FDG	fluorodeoxyglucose (18F)
FISH	fluorescence in-situ hybridization,
FSH	follicle-stimulating hormone
G-CSF	granulocyte colony-stimulating factor
GGT	gamma-glutamyltransferase
GCP	Good Clinical Practice
GLP	Good Laboratory Practice
GM-CSF	granulocyte-macrophage colony-stimulating factor
HBc antibody	anti-hepatitis B core antibody
HbsAg	hepatitis B surface antigen
HBV	hepatitis B virus
HCV	hepatitis C virus
hERG	human ether-à-go-go-related gene
HL	Hodgkin lymphoma
HIV	human immunodeficiency virus
HRQL	health-related quality of life
IB	Investigator's Brochure
ICH	International Conference on Harmonisation
ICMJE	International Committee of Medical Journal Editors
IEC	independent ethics committee
Ig	immunoglobulin (including subtypes A, E, G, and M)
IgHV	immunoglobulin heavy chain variable region
IND	Investigational New Drug (application)
iNHL	indolent non-Hodgkin lymphoma
INR	international normalized ratio
IRB	institutional review board
IRC	independent review committee

---

ITT	intention to treat
IUD	intrauterine device
IWCLL	International Workshop on CLL
IWRS	interactive web response system
JAK	Janus kinase
K 2 -EDTA	potassium-ethylenediaminetetraacetic acid
LD	longest diameter
LDH	lactate dehydrogenase
LH-RH	luteinizing hormone-releasing hormone
LLN	lower limit of normal
LPD	longest perpendicular diameter
LVD	longest vertical dimension
MTD	maximum tolerated dose
MCL	mantle cell lymphoma
MDR	multi-drug resistance
MedDRA	Medical Dictionary for Regulatory Activities
MRI	magnetic resonance imaging
mTOR	mammalian target of rapamycin
ND	no disease
NHL	non-Hodgkin lymphoma
OAT	occluded artery trial
OCT	organic cation transporter
ORR	overall response rate
OS	overall survival
pAKT	phosphorylated AKT
PCR	polymerase chain reaction
PD	progressive disease
PET	positron-emission tomography
Pgp	P-glycoprotein
PI3K	phosphatidylinositol 3-kinase
PI3K $\delta$	phosphatidylinositol 3-kinase p110 $\delta$ isoform
PJP	Pneumocystis jirovecii pneumonia
PFS	progression-free survival
PML	progressive multifocal leukoencephalopathy
PP	per protocol
PPD	product of the perpendicular diameters
PRO	patient-reported outcome
PR	partial response
PT	prothrombin time
PVA	polyvinyl alcohol

QD	once per day
QT (interval)	measure of time between start of Q wave and end of T wave in electrical cycle of heart
RNA	ribonucleic acid
SAE	serious adverse event
SADR	serious adverse drug reaction
SD	stable disease
SJS	stevens-johnson syndrome
SPD	sum of the products of the perpendicular diameters of measured lymph nodes
SUSAR	suspected, unexpected, serious adverse reaction
SYK	spleen tyrosine kinase
$t_{1/2}$	half-life
$T_{max}$	time of maximum concentration
TEN	toxic epidermal necrolysis
TTR	time to response
UGT	uridine 5'-diphospho-glucuronosyltransferase
ULN	upper limit of normal
WHODRUG	World Health Organization Drug Dictionary
ZAP=70	zeta-associated protein 70

